**Figure 3. Enrichment Strategy Study Design**

## 14.2 Definitions of Study Populations

- 1) The “Intent-to-Treat (ITT) Population” – All subjects who may have taken at least one dose of lorcaserin or placebo after randomization on Study Day 8. This includes all subjects who receive at least one bottle of study drug (lorcaserin or placebo) after randomization on Study Day 8, with the exception of any subjects who return the full bottle before leaving the clinic on Study Day 8 (this may occur, for example, if a subject changes his/her mind about continuing in the study).
- 2) The “PPEE Population” – The subset of the ITT Population who prequalify for the primary efficacy endpoint by meeting the specified PPEE criteria prior to randomization.
- 3) The “Non-PPEE Population” – The subset of the ITT Population who fail to meet the specified PPEE criteria and, therefore, do not prequalify for the primary efficacy endpoint.

- 4) The “Non-Drinker Population” – The subset of the ITT Population who are non-drinkers, as evidenced by 100% negative results for the presence of EtG in urine from the beginning of screening through the urine test on Study Day 8, prior to randomization and 2) consistent self-report of no alcohol use throughout this same period of time, as well as the 30 days prior to screening.
- 5) The “Attempting Alcohol Abstinence (AAA) Population” – The subset of the ITT Population who: 1) fail to meet criteria for the “Non-Drinker Population” and 2) commit to quitting drinking during the study, as evidenced by viewing the optional Quit to Quit module on Study Day 8 prior to randomization.
- 6) The “Baseline Low Use/Adherent Population” – The subset of the non-PPEE Population who failed to qualify for the primary efficacy endpoint only because they reported <8 days of cocaine use during the 30 days prior to screening (plasma acetazolamide level on Study Day 8 was  $\geq 15$  ng/mL).
- 7) The “Baseline Adherent Population” – The combination of the PPEE Population and the Baseline Low Use/Adherent Population (all subjects with Study Day 8 plasma acetazolamide levels  $\geq 15$  ng/mL).
- 8) The Baseline Non-Adherent Population – The subset of the ITT Population who are not part of the Baseline Adherent Population (all subjects with Study Day 8 plasma acetazolamide levels <15 ng/mL).
- 9) The “Acetazolamide Safety Population” – All subjects who participate in the 1-week, single-blind run-in period. Note: Treatment-emergent AEs recorded during this period will be assessed in relationship to acetazolamide.
- 10) The “Lorcaserin/Placebo Safety Population” – The same group of subjects defined above for the ITT Population. Note: Treatment-emergent AEs recorded in this group after randomization will be assessed in relationship to lorcaserin/placebo.

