### **12.3 Smoking and Alcohol History**

The Smoking History Survey is a modified version of the Mayo Nicotine Dependence Center Patient Questionnaire (1991) and will be administered by a research assistant. The Smoking History Survey asks subjects the following: how many cigarettes per day they smoke and how many times they have attempted to quit (including methods). Information on other non-cigarette tobacco products is also noted. Subjects will also be asked about their alcohol consumption during the last 30 days: how many days did they have at least one drink; how many drinks did they usually have on the days they drank; and the largest number of drinks consumed on any one day during the 30-day period.

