While 272 subjects will be enrolled in the current study, it is estimated that 180 subjects (approximately 90 subjects per group) will meet criteria for inclusion in the PPEE population. Assuming 6% and 20% success rates (for achieving abstinence from cocaine) during placebo and lorcaserin treatment, respectively, 90 subjects per group in the PPEE population would yield 80% power (Pearson’s Chi-square test for two proportions; two-sided comparison, alpha = 0.05). The assumption of 6% success in the placebo group is based on results from similar cocaine medication trials conducted by NIDA in the past, using the same definition of “success” (placebo group success rates have ranged from 0 to 9%). The goal of 20% success in the lorcaserin group would constitute slightly more than a three-fold increase in success compared to the expected placebo success rate. Such efficacy would be clinically meaningful. No medications are currently approved for the treatment of cocaine use disorder, but a 3-fold increase in quit rate (vs. placebo) would constitute greater efficacy than has been observed for FDA-approved smoking cessation medications. A recent meta-analysis of randomized, placebo-controlled smoking cessation trials (Eisenberg *et al.*, 2008) revealed that placebo and bupropion quit rates were 11% and 20%, respectively (16 trials), placebo and nicotine gum quit rates were 14% and 19%, respectively (22 trials), placebo and nicotine patch quit rates were 7.5% and 13%, respectively (30 trials), and placebo and varenicline quit rates were 15% and 26%, respectively (13 trials). For the current study, multiple factors were considered in estimating that 180 of the 272 enrolled subjects will qualify for inclusion in the PPEE population. Further explanation requires an understanding of enrichment strategy details.

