The second criterion for inclusion in the PPEE population is focused on cocaine use self-report data collected during the first day of screening. To be included in the PPEE population, subjects must report using cocaine on at least 8 days during the 30 days immediately prior to screening. Subjects reporting 1 to 7 days of cocaine use will still be enrolled, and their data will be evaluated for exploratory efficacy endpoints, but they will not qualify for the PPEE population. In an unpublished evaluation of recent NIDA-sponsored cocaine medication trials, higher placebo success rates were observed for subjects reporting <8/30 days of cocaine use immediately prior to screening. For example, in a trial evaluating nopicastat vs. cocaine dependence (manuscript in preparation), 18% of placebo subjects reporting <8/30 days of cocaine use prior to screening were successful in achieving 3 weeks of abstinence at the end of the study, whereas only 6% of placebo subjects reporting >7/30 days of cocaine use prior to screening were able to achieve this same duration of abstinence. In the nopicastat trial, 22% of enrolled subjects reported <8/30 days of cocaine use. Based on this experience, we estimate that approximately 22% of subjects who enroll in the current trial will report <8/30 days of cocaine use prior to screening and, therefore, will not qualify for the PPEE population.

In addition to subjects failing to meet the two criteria mentioned above, it is anticipated on the basis of past experience that approximately 5% of subjects who are enrolled in the current study will drop out prior to randomization on Study Day 8 (a 5% dropout rate was seen during the first week of the NIDA nopicastat trial).

[figure not shown]
With the above factors in mind, the estimated size of the PPEE population can be addressed. If 272 subjects are enrolled and 22% (60) report <8/30 days cocaine use (excluding them from the PPEE population), 212 subjects remain eligible. If approximately 10% (22) of the remaining 212 subjects fail to qualify for the PPEE population based on nonadherence during the run-in period (Study Day 8 plasma acetazolamide <15 ng/mL), 190 subjects remain eligible. If approximately 5% (10) of the remaining 190 subjects drop out prior to Study Day 8, 180 subjects will qualify for the PPEE population.

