k) The proportion of subjects successfully achieving abstinence from alcohol during the last three weeks of treatment (Study Weeks 11-13) in the subset of the AAA Population who are also in the Baseline Adherent Population and who received a diagnosis of Alcohol Use Disorder (AUD) during screening. Comparison of this proportion in subjects receiving lorcaserin vs. placebo will constitute the analysis. A subject will be regarded as abstinent from alcohol during the last three weeks of treatment if:

- There are self-report data indicating no alcohol use on each day of the 3-week period;
- There is at least one ethyl glucuronide (EtG) assay result for a urine sample collected within the 3-week period; and
- EtG assay results are negative (EtG < 500 ng/mL) for all urine samples collected during the 3-week period.

Subjects not meeting these three criteria (including dropouts) will be regarded as having failed to achieve abstinence from alcohol.

- l) The proportion of subjects successfully achieving abstinence from alcohol during the last three weeks of treatment (Study Weeks 11-13) in the subset of the AAA Population who are also in the Baseline Adherent Population. Comparison of this proportion in subjects receiving lorcaserin vs. placebo will constitute the analysis. Abstinence from alcohol will be defined as described above. (Note: attempting alcohol abstinence and good baseline adherence +/- AUD)
- m) The proportion of subjects successfully achieving abstinence from alcohol during the last three weeks of treatment (Study Weeks 11-13) in the subset of the AAA Population who received a diagnosis of AUD during screening. Comparison of this proportion in subjects receiving lorcaserin vs. placebo will constitute the analysis. Abstinence from alcohol will be defined as described above. (Note: attempting alcohol abstinence with AUD +/- good baseline adherence)
- n) The proportion of subjects successfully achieving abstinence from alcohol during the last three weeks of treatment (Study Weeks 11-13) in the subset of the ITT Population who received a diagnosis of AUD during screening. Comparison of this proportion in subjects receiving lorcaserin vs. placebo will constitute the analysis. Abstinence from alcohol will be defined as described above. (Note: includes all subjects with AUD whether or not trying to abstain from alcohol)

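### Exploratory alcohol endpoint (l), and to a lesser degree (k), (m) and (t), set no minimum baseline drinking, so rare drinkers can count as successes without any change in drinking

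*Combined protocol and SAP*

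**What the plan says.** Section 14.2, item 5, gives the AAA Population two conditions. Its members "fail to meet criteria for the “Non-Drinker Population” and 2) commit to quitting drinking during the study", and the second condition is judged "as evidenced by viewing the optional Quit to Quit module on Study Day 8 prior to randomization". Item 4 makes a Non-Drinker someone with every EtG result negative from the start of screening through Day 8 and no reported alcohol over that period and the 30 days before it. One reported drinking day or one positive EtG therefore ends Non-Drinker status. No drinking frequency is named.

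Section 14.3.3 defines alcohol success over Weeks 11-13 by three conditions: "There are self-report data indicating no alcohol use on each day of the 3-week period", at least one EtG result, and every EtG result negative. Dropouts count as failures. The populations differ:

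- (l): AAA and run-in adherent, described as "attempting alcohol abstinence and good baseline adherence +/- AUD".
- (k): as (l), plus an alcohol use disorder (AUD) diagnosis.
- (m): AAA plus AUD.
- (t): as (k), over six weeks.
- (n): ITT plus AUD; AAA not required.
- (o) and (p): the whole ITT Population.

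Section 12.3 collects, for the last 30 days, "how many days did they have at least one drink". No alcohol endpoint uses that count. For cocaine, section 14.1 does set a floor for the primary population: "subjects must report using cocaine on at least 8 days during the 30 days immediately prior to screening". Its reason is a previous trial in which placebo success was 18% below the floor and 6% above it.

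**The concern.** For AAA the entry threshold (any drinking) and the success threshold (no drinking for three weeks) lie next to each other, and nothing links success to where the subject started. Someone who drinks once a month can meet both without changing. A quit rate reported for (l) then mixes people who stopped drinking with people who rarely drank. The plan recognised the same problem for cocaine and excluded low-frequency users from its primary population.

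What is at stake is how the alcohol results read. The synopsis singles out alcohol abstinence as an exploratory question of importance, so these rates are likely to be reported.

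**Working it through.** **1. The plan's own figure.** No alcohol endpoint has a stated sample size, power or expected rate. The only powered comparison is the cocaine primary endpoint: "Assuming 6% and 20% success rates (for achieving abstinence from cocaine) during placebo and lorcaserin treatment, respectively", for which "90 subjects per group in the PPEE population would yield 80% power (Pearson’s Chi-square test for two proportions; two-sided comparison, alpha = 0.05". With pooled proportion 0.13:

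- z = [0.14 − 1.96·√(2·0.13·0.87/90)] / √[(0.06·0.94 + 0.20·0.80)/90] = (0.14 − 0.0983)/0.0490 = 0.85
- power = 80.3%, so the figure reproduces.

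**2. Chance success at a given drinking frequency.** Assume d drinking days per 30, independent days and no change. The chance of w drink-free days is (1 − d/30)^w.

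| d per 30 | 21 days: (k), (l), (m) | 42 days: (t) |
|---|---|---|
| 1 | 49% | 24% |
| 2 | 23% | 5.5% |
| 3 | 11% | 1.2% |
| 4 | 5% | 0.25% |
| 8 | 0.15% | about 0% |

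The baseline window is longer than 30 days: 30 before screening, 1 to 21 of screening and 7 of run-in, so about 38 to 58. With one drinking day in that whole window, the 21-day chance is (1 − 1/38)^21 = 57% to (1 − 1/58)^21 = 69%.

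Independence matters. If exactly d days fall at random in each 30-day block and the 21 days lie within one block, the chance is C(30−d,21)/C(30,21): 30% at d = 1, 8.3% at 2 and 0.5% at 4. Clustered drinking would push the other way.

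**3. Averaged over a drinking mix (assumed).** Let the daily probability p follow Beta(a,b), with at least one drinking day among 30. Write E(n) for the mean of (1 − p)^n. No-effect success over 21 days is [E(21) − E(51)] / [1 − E(30)]. For Beta(1,2), E(n) = 2/(2+n), which gives (0.0870 − 0.0377)/0.9375 = 5.2%. All five mixes:

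| Mix | Mean days/30 | Share with 1-3 days | 21 days | 42 days |
|---|---|---|---|---|
| Beta(1,2) | 10.7 | 19% | 5.2% | 2.0% |
| Beta(0.7,1.5) | 10.7 | 22% | 7.1% | 3.1% |
| Beta(1,3) | 8.3 | 26% | 7.6% | 2.9% |
| Beta(2,3) | 12.1 | 8% | 1.6% | 0.4% |
| Beta(3,4) | 12.9 | 4% | 0.6% | 0.1% |

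In the three mixes above 5%, 83% to 87% of chance successes come from subjects with 1-3 days. At 8 or more days the rate is below 0.2% in every mix. These figures assume full retention and complete daily reports. At an assumed 70% retention the 21-day range becomes 0.4% to 5.3%.

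**4. Effect on the contrast (assumed rates).** If true quit rates are q0 and q1 and chance success c is independent of quitting, each observed rate is q + (1 − q)c and the difference is (q1 − q0)(1 − c). Take 10% against 30%:

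- c = 0.6%: 10.6% against 30.4%, difference 19.9 points.
- c = 7.6%: 16.9% against 35.3%, difference 18.5 points.

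A harsher case lets rare drinkers gain nothing from the drug. Borrow 6% against 20% and 90 per arm from the cocaine calculation, and let 10% of subjects succeed at 50% in both arms. The rates become 10.4% and 23.0%, and power falls from 80% to 62%.

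**5. Gain from adjustment (assumed).** Simulations of 110 AAA subjects (10% against 30% quitting plus chance success) compared the unadjusted test with one adjusted for log(days + 1). When quitting is unrelated to baseline drinking, the gain ranged from none to about 2.7 power points. When baseline drinking also predicts quitting, it was about 1 to 7.

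**The case against.** The strongest reply is that the plan already narrows the alcohol population. (k), (m) and (t) require an AUD diagnosis, (k), (l) and (t) require run-in adherence, all four require the Day 8 opt-in, and (t) needs six weeks. Comparing (k) with (l) already shows what dropping the AUD requirement does. This stands, and it confines the clearest exposure among the AAA endpoints to (l). An AUD diagnosis carries no drinking-day floor in these documents, so the mechanism is reduced in the other three, not removed.

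A reader might infer that the arms are compared unfairly. The documents do not support that. Membership is fixed before randomisation, and section 7 stratifies by module viewing and by alcohol and/or sedative use disorder, so chance successes are expected equally in both arms.

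A reader might also infer that the plan adjusts for nothing. Section 14 names no covariate for these endpoints, but it defers several details to a Statistical Analysis Plan, and no separate one is in the document. Only the narrower statement is safe.

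The size is also open to challenge: the drinking mix, the AAA size and the alcohol quit rates are all assumed, and the power gain is small. That stands. So does the point that an 8-day cut comes from cocaine data and would put 1-3 day drinkers in the same band as 4-7 day drinkers, whose chance success is far lower.

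**Conclusion.** The point holds as a minor improvement to exploratory analyses. Endpoint (l), and to a lesser degree (k), (m) and (t), can count unchanged rare drinkers as successes. The probability is substantial at 1-3 days per 30 and negligible at 8 or more, so it would be wrong to say that infrequent drinkers as a class become responders, or that every alcohol endpoint admits anyone with one drinking day.

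Across an AAA set the no-effect success rate is about 0.6% to 8% under the assumed mixes, and lower with dropout or over six weeks. Those mixes describe drinkers generally and do not quantify the AUD-restricted endpoints. The consequence is a raised quit rate and some dilution, without bias between arms. The primary and secondary cocaine conclusions are untouched.

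(o) and (p) are more exposed on the same reasoning, because baseline Non-Drinkers are in the denominator and can count as successes.

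**What to change.** In the SAP, before unblinding:

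- For (k), (l), (m) and (t), adjust the lorcaserin-placebo comparison for the section 12.3 count of drinking days in the 30 days before screening. Use a logistic model with treatment and log(days + 1), and obtain the arm difference by standardisation. Show the raw proportions beside it.
- Tabulate success by arm and baseline drinking days, descriptively, with a low band that isolates 1-3 days (for example 0, 1-3, 4-7, 8 or more). Give the same table for (o) and (p).

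The cost is SAP wording and one variable already collected; no population or endpoint changes. The expected gain is roughly 0.5 to 3 power points, more if baseline drinking also predicts quitting. The main benefit is a quit rate that can be interpreted. There are two drawbacks. The estimate becomes model-based in a small exploratory set. The section 12.3 count also misses drinking during screening and run-in, so some AAA subjects will have a count of zero. Bands chosen after unblinding would be post hoc.

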### **14.3 Outcome Measures**

#### **14.3.1 Primary Efficacy Outcome Measures**

The primary endpoint is the proportion of subjects successfully achieving abstinence from cocaine during the last three weeks of treatment (Study Weeks 11-13) in the PPEE population. Comparison of this proportion in subjects receiving lorcaserin vs. placebo will constitute the primary endpoint analysis.

A subject will be regarded as a treatment success (abstinent from cocaine during the last three weeks of treatment) if:

- There are self-report data indicating no cocaine use on each day of the 3-week period;
- There is at least one benzoylecgonine (BE) assay result for a urine sample collected within the 3-week period; and

- BE assay results are negative (BE <150 ng/mL) for all urine samples collected during the 3-week period.

Subjects not meeting these three criteria (including dropouts) will be regarded as treatment failures.

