## **7 STUDY DESIGN**

This is a 19-week, multi-center, parallel group study that includes: 1) up to 3 weeks for screening; 2) a 13-week Treatment Phase consisting of a 1-week, single-blind run-in period, when all subjects receive twice daily 15 mg acetazolamide capsules (a medication adherence marker), followed by randomization to either twice daily 10 mg lorcaserin or placebo capsules for the remaining 12 weeks; and 3) a 3-week follow-up period, with scheduled visits during Study Weeks 14 and 16.

Upon providing informed consent, subjects will be screened over a period of up to 21 days and will complete baseline evaluations. Subjects who complete all screening and baseline evaluations and meet the specified inclusion/exclusion criteria will be eligible to enter the treatment phase. Eligible subjects will receive 15 mg BID acetazolamide during the 1-week run-in period, which will be used to define the PPEE population (on the basis of plasma acetazolamide concentrations  $\geq 15$  ng/mL and self-report of cocaine use on at least 8 days during the 30 days immediately prior to screening). Following the 1-week run-in period, all subjects will be randomly assigned to receive either placebo or 10 mg BID lorcaserin for 12 weeks, with weekly clinic visits during those 12 weeks, and with follow-up assessments 1 and 3 weeks after treatment completion.

A randomized block design within each site will be utilized with the following stratification factors:

- a. Number of subject-reported cocaine use days during the 30 days immediately prior to screening (<8 days versus 8 or more days);
- b. Continued viewing of the computer-based alcohol intervention on Study Day 8 (yes/no);
- c. Diagnosis of Alcohol Use Disorder and/or Sedative, Hypnotic, or Anxiolytic use disorder (yes/no).

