### **14.3.2 Secondary Efficacy Outcome Measures**

The secondary endpoint is the proportion of subjects successfully achieving abstinence from cocaine during the last three weeks of treatment (Study Weeks 11-13) in the subset of the PPEE population who are also part of the Non-Drinker Population or the AAA Population. Comparison of this proportion in subjects receiving lorcaserin vs. placebo will constitute the secondary endpoint analysis. Abstinence will be defined as described for the primary endpoint.

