### **14.3.3 Exploratory Outcome Measures**

- a) The proportion of subjects successfully achieving abstinence from cocaine during the last three weeks of treatment (Study Weeks 11-13) in the ITT population. Comparison of this proportion in subjects receiving lorcaserin vs. placebo will constitute the analysis. Abstinence will be defined as described for the primary endpoint. (Note: what the primary endpoint would have been if there were no enrichment strategy)
- b) The proportion of subjects successfully achieving abstinence from cocaine during the last three weeks of treatment (Study Weeks 11-13) in the subset of the ITT population who are also part of the Non-Drinker population or the AAA Population. Comparison of this proportion in subjects receiving lorcaserin vs. placebo will constitute the analysis. Abstinence will be defined as described for the primary endpoint. (Note: what the secondary endpoint would have been if there were no enrichment strategy)
- c) The proportion of subjects successfully achieving abstinence from cocaine during the last three weeks of treatment (Study Weeks 11-13) in the non-PPEE population. Comparison of this proportion in subjects receiving lorcaserin vs. placebo will constitute the analysis. Abstinence will be defined as described for the primary endpoint.
- d) The proportion of subjects successfully achieving abstinence from cocaine during the last three weeks of treatment (Study Weeks 11-13) in the subset of the non-PPEE population who are also part of the Non-Drinker population or the AAA Population. Comparison of this proportion in subjects receiving lorcaserin vs. placebo will constitute the analysis. Abstinence will be defined as described for the primary endpoint.
- e) The proportion of subjects successfully achieving abstinence from cocaine during the last three weeks of treatment (Study Weeks 11-13) in the Baseline Low Use/Adherent Population. Comparison of this proportion in subjects receiving lorcaserin vs. placebo will constitute the analysis. Abstinence will be defined as described for the primary endpoint. (Note: similar to primary endpoint but in subjects excluded from the PPEE population only because of low baseline cocaine use)
- f) The proportion of subjects successfully achieving abstinence from cocaine during the last three weeks of treatment (Study Weeks 11-13) in the subset of the Baseline Low Use/Adherent Population who are also part of the Non-Drinker population or the AAA Population. Comparison

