of this proportion in subjects receiving lorcaserin vs. placebo will constitute the analysis. Abstinence will be defined as described for the primary endpoint. (Note: similar to secondary endpoint but in subjects excluded from the PPEE population only because of low baseline cocaine use)

g) The proportion of subjects successfully achieving abstinence from cocaine during the last three weeks of treatment (Study Weeks 11-13) in the Baseline Adherent Population. Comparison of this proportion in subjects receiving lorcaserin vs. placebo will constitute the analysis. Abstinence will be defined as described for the primary endpoint. (Note: what the primary endpoint would have been if low baseline cocaine use had not excluded subjects from the PPEE Population)

h) The proportion of subjects successfully achieving abstinence from cocaine during the last three weeks of treatment (Study Weeks 11-13) in the subset of the Baseline Adherent Population who are also part of the Non-Drinker population or the AAA Population. Comparison of this proportion in subjects receiving lorcaserin vs. placebo will constitute the analysis. Abstinence will be defined as described for the primary endpoint. (Note: what the secondary endpoint would have been if low baseline cocaine use had not excluded subjects from the PPEE Population)

i) The proportion of subjects successfully achieving abstinence from cocaine during the last three weeks of treatment (Study Weeks 11-13) in the subset of the AiView Users Population who are also part of the PPEE Population. Comparison of this proportion in subjects receiving lorcaserin vs. placebo will constitute the analysis. Abstinence will be defined as described for the primary endpoint.

j) The proportion of subjects successfully achieving abstinence from cocaine during the last three weeks of treatment (Study Weeks 11-13) in the subset of the AiView Non-Users Population who are also part of the PPEE Population. Comparison of this proportion in subjects receiving lorcaserin vs. placebo will constitute the analysis. Abstinence will be defined as described for the primary endpoint.

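### Randomisation is stratified on three factors, but no between-group comparison in the document uses any of them; naming a stratified primary test would be a cheap, small improvement

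*Combined protocol and SAP*

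**What the plan says.** Section 7 states: "A randomized block design within each site will be utilized with the following stratification factors". The factors are (a) fewer than 8 versus 8 or more cocaine-use days in the 30 days before screening, (b) whether the subject continues the alcohol modules on Study Day 8, and (c) an alcohol or sedative-class diagnosis. The Synopsis lists the same three but words (c) differently. It refers to dependence on alcohol or benzodiazepines, where Section 7 refers to use disorder and to the wider sedative, hypnotic or anxiolytic class.

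Section 14.3.1 gives the primary analysis as: "Comparison of this proportion in subjects receiving lorcaserin vs. placebo will constitute the primary endpoint analysis". Sections 14.3.2 and 14.3.3 repeat that form for the secondary and most exploratory outcomes. The only between-group test named for this trial is in the sample-size text of Section 14.1: "Chi-square test for two proportions; two-sided comparison, alpha = 0.05".

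Some factors decide who is analysed. Use days fixes membership of the PPEE population (Section 14.1). Module viewing defines the AAA population, whose members "commit to quitting drinking during the study, as evidenced by viewing the optional Quit to Quit module on Study Day 8 prior to randomization" (Section 14.2). Alcohol use disorder, one part of factor (c), selects the subjects for exploratory k, m, n and t.

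Section 14.1 also reports that in an earlier trial "18% of placebo subjects reporting <8/30 days of cocaine use prior to screening were successful in achieving 3 weeks of abstinence", against 6% of those with more use days.

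**The concern.** The sponsor judged three factors important enough to balance at randomisation, yet the text does not carry them into any comparison. Using a factor to choose an analysis set restricts who is compared; it does not adjust the comparison. When arms are balanced within prognostic strata, the variation between strata drops out of the treatment difference. The Pearson test still counts it in its variance, so the test runs below its nominal level and gives up some power.

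The matter also bears on how fully the primary analysis is specified. Section 14.3.1 names no test, stratum or effect measure, and few events are expected: 0.06 × 90 = 5.4 successes on placebo and 0.20 × 90 = 18 on lorcaserin. Fixing the test and its strata in advance removes a choice that would otherwise be open at analysis.

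**Working it through.** **Stated power.** Inputs from Section 14.1: 90 per group, 6% versus 20%, two-sided alpha 0.05. With mean rate 0.13:

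z = [0.14 × √90 − 1.96 × √(2 × 0.13 × 0.87)] / √(0.06 × 0.94 + 0.20 × 0.80) = (1.328 − 0.932) / 0.465 = 0.851, so power = 80.3%.

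The stated 80% reproduces with no stratification. Exact Pearson power is 82.3%. Exact size is 4.4% at 6% in both arms and 5.0% at 13% in both arms.

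**Which factors can be used where.** Every PPEE subject has 8 or more use days, so factor (a) is constant there and only (b) and (c) vary. Factor (a) does vary in the ITT population (exploratory a) and the Baseline Adherent population (exploratory g).

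**Documented prognostic strength.** For use days, the odds ratio is (0.18/0.82) / (0.06/0.94) = 3.44. The document gives no such figure for (b) or (c), so a range of 1 to 3.44 per factor is assumed for them.

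**Primary comparison.** The CMH statistic is [Σ(x₁ − m·n₁/N)]² / Σ[n₁n₀m(N − m) / (N²(N − 1))], summed over strata. In each stratum, x₁ is lorcaserin successes, m total successes, n₁ and n₀ the arm sizes, and N = n₁ + n₀. No continuity correction is used. Simulated with 180 subjects, four roughly equal strata, arms balanced within strata, marginal rates 6% and 20%, and 200,000 trials per case:

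| Assumed odds ratio per factor | Pearson power | CMH power | Difference |
|---|---|---|---|
| 1 | 82.2% | 82.3% | +0.1 |
| 2 | 82.6% | 83.2% | +0.6 |
| 3.44 | 83.3% | 85.0% | +1.7 |

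Across other runs with different stratum sizes, the gain at 3.44 was 1.3 to 2.2 points. Type I error at 6% in both arms was 4.0 to 4.7% for Pearson and about 4.4 to 4.9% for CMH.

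A less tidy version used 258 randomised subjects, 10 sites, assumed blocks of 4, 50% prevalence of each factor, and 10% removed for low acetazolamide. The differences were −0.3, −0.1, +0.5 and +1.7 points at odds ratios 1, 1.5, 2 and 3.44. There the type I errors lie closer together: Pearson 4.6 to 4.9%, CMH 4.7 to 5.0%. Coverage of the 95% interval for the Mantel-Haenszel risk difference was 94.6 to 95.2%.

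**Site.** Ten sites × 8 cells = 80 cells for about 258 randomised subjects, or 3.2 per cell. In PPEE, 10 × 4 = 40 cells for 180, or 4.5 per cell. Stratifying by site as well would be too sparse, which is why the test pools over sites.

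**Exploratory a and g, stratified by use days.** Sizes: 272 × 0.95 = 258 (ITT) and 258 × 0.90 = 232 (Baseline Adherent), with 22% below 8 days and placebo rates of 18% and 6%. The overall placebo rate is 0.22 × 0.18 + 0.78 × 0.06 = 8.64%. Its binomial variance is 0.0864 × 0.9136 = 0.0789. The within-stratum variance is 0.22 × 0.18 × 0.82 + 0.78 × 0.06 × 0.94 = 0.0765, about 3% less.

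| ITT, assumed common treatment odds ratio | Pearson power | CMH power | Difference |
|---|---|---|---|
| 2 | 39.3% | 41.0% | +1.7 |
| 2.5 | 64.8% | 66.8% | +2.0 |
| 3 | 82.7% | 84.1% | +1.4 |

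Type I error in ITT is 4.7% for Pearson and 5.0% for CMH. In the Baseline Adherent population the gains are 1.4 to 1.9 points. If the effect is confined to subjects with 8 or more days, the gain in either population is only about 0.2 to 0.3 point.

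**Secondary set.** The analysis is "in the subset of the PPEE population who are also part of the Non-Drinker Population or the AAA Population", and the size of that subset is not given. Stratifying it by (c), at factor odds ratios of 1 to 3.44, CMH was lower than Pearson at every value tried if the set has 80 subjects (by 0.1 to 1.5 points). The difference was +0.1 to +1.4 at 110 subjects and −0.2 to +1.0 at 140.

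**The case against.** The strongest reply is that nothing here is an error. The unadjusted test is valid, does not inflate type I error and delivers the stated power. The only factor documented as prognostic is constant in the primary population, so the primary gain rests on assumed odds ratios; the largest figure borrows 3.44 from the factor that cannot be used there. In the version with sites and small blocks, the change is slightly negative when (b) and (c) carry little or no information. All of this stands, and it is why the point is minor.

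A second reply is that Section 15.3 refers to a Statistical Analysis Plan, and the adjustment may be set out there. No separate SAP text appears in the combined document, so the gap is shown only for the text available. However, where Section 14.3.3 defers to the SAP it names the item: the expected plasma range, the cigarette analysis and the acetazolamide-adherence analysis. Neither the primary test nor stratification is among them.

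A reader might infer that the plan commits to an unadjusted primary test. It does not: Section 14.1 uses Pearson for sample size, and Section 14.3.1 names no test. A reader might also infer that the trial is underpowered, or that the 18% versus 6% contrast shows a loss in the primary analysis. The power figure reproduces, and that contrast cannot operate within PPEE.

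Finally, leaving site out and using different strata for different analyses is pragmatic, not a rule that the plan has broken. That is fair. Sparse cells justify the first, and documented prognosis guides the use of use days in a and g.

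**Conclusion.** The concern holds as a minor, low-cost improvement. In the available text no between-group comparison uses a randomisation factor as a stratum or covariate, and the primary test is not named where the primary analysis is defined.

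The best-supported benefit is in exploratory a and g. The document describes these as "what the primary endpoint would have been if there were no enrichment strategy" and "what the primary endpoint would have been if low baseline cocaine use had not excluded subjects from the PPEE Population", which makes them natural checks on the enriched result. The gain there, about 1.4 to 2 points of power, assumes a common treatment odds ratio of 2 to 3 and that the earlier trial's placebo rates carry over. It nearly vanishes if the effect is confined to heavier users.

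For the primary analysis the change is about 0 to +2 points over assumed odds ratios of 1 to 3.44 per factor, with a possible loss of about 0.3 point if neither factor is prognostic. The sample size need not change. The calculations do not support requiring stratification for the secondary endpoint.

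**What to change.** - In Section 14.3.1, name the primary PPEE test: a two-sided CMH test at alpha 0.05 without continuity correction, stratified by Day 8 module viewing and alcohol/sedative disorder (four strata) and pooled over sites. Report a Mantel-Haenszel risk difference with its 95% confidence interval. Keep the Pearson chi-square as a sensitivity analysis.
- For exploratory a and g, stratify by fewer than 8 versus 8 or more use days.
- Do not require stratification for the secondary endpoint or the smaller exploratory subsets.
- Reconcile the wording of factor (c) in the Synopsis and Section 7 with the definition programmed in the randomisation system before using it as a stratum.
- If the SAP already specifies the test and its strata, a cross-reference in Section 14.3.1 closes the first item.

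The cost is protocol and SAP wording and a few lines of code, with no new data or subjects. The drawback is a few sparse strata, and no gain or a very small loss if the factors turn out not to be prognostic.
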